6.1.6. Pooling of Sites

Not applicable; sites are pooled into regions as part of randomization stratification.

6.1.7. Derived Variables

- **Day 1** = First day of Treatment (Placebo or Dasiglucagon) during Part 1. Study day will be calculated with respect to Day 1.
- **Treatment period**

As primary and secondary endpoint assessments are not performed at planned visits but continuously during the study, we have to define treatment periods. Those will then be used to assign a treatment period to an evaluation.

Treatment periods created will be:

- Part 1 – Treatment period 1: First 48-hours treatment period
- Part 1 – Treatment period 2: Second 48-hours treatment period
- Part 1 – Last 12 hours per treatment period
- Part 2

[Table 4](#) describes the derivation for each of those treatment periods.

Table 4: Derivation of Treatment Periods

Part	Time Point	Treatment Period (TP)	Start date	End date
Part 1		TP1	Day 1	Last exposure treatment period 1
		TP2	First exposure treatment period 2	Last exposure treatment period 2
Part 1	Last 12-hour/24-hour per TP	TP1	End date minus 12 hours/24 hours	Last exposure treatment period 1
		TP2	End date minus 12 hours/24 hours	Last exposure treatment period 2
Part 2			Day 5 first exposure	End of study exposure

Abbreviations: TP1 = treatment Part 1, TP2 = treatment Part 2

- **Study Week:** to be defined for Part 2 only
 - A 7-day period derived for displays of events related to CGM and/or SMPG results, gastric carbohydrate administrations, health care outcomes, and other assessments that may occur between clinic visits where a defined study week is needed.

The study weeks will be derived as follows:

Table 5: Study weeks

Study Week	Start	End
Week 1	Day 5 first exposure	Start + 167 hours 59 minutes
Week 2	End date week 1 + 1 minute	Start + 167 hours 59 minutes
Week 3	End date week 2 + 1 minute	Start + 167 hours 59 minutes

- **Change from baseline** = value at current time point – value at baseline.
- **TEAE** = an AE with an onset at the time of or following the start of treatment with the trial drug (dasiglucagon or placebo) through the Follow-up visit or Early Termination visit, whichever occurs first.
- **Weighted Mean IV GIR:** AUC will be calculated using linear trapezoidal method and divided by the length of the time period in minutes. The weighted mean IV GIR endpoint is expressed as glucose in mg/kg/min. This will be calculated over last 12 hours of each treatment period and over last 48 hours of each treatment period during Part 1.
- **Weighted Mean IV GIR threshold:** This variable will be assigned “Yes” when the Weighted Mean IV GIR calculated over 12 hours period is not missing and < 10mg/kg/min and will be assigned “No” when value calculated will be $\geq 10\text{mg/kg/min}$.
- **Z-scores:** For subjects who are less than 2 years of age, WHO growth charts will be used to calculate Z-scores, as described here: 'www.cdc.gov/nccdphp/dnpao/growthcharts/resources/sas-who.htm'. For subjects who are greater than or equal to 2 years of age, Z-scores will be derived based on the SAS program in link 'www.cdc.gov/nccdphp/dnpao/growthcharts/resources/sas.htm' by using SEXN, Age in months ((VSDAT-ADSL.BRTHDT)/30.4375) and corresponding weight/height at baseline measurements.

- **PK Clearance:**

$$CL/f \text{ (L/h)} = R_0/C_{ss}$$

where R_0 = infusion rate (pmol/h) and C_{ss} = concentration at steady state (pmol/L), weight
($1\mu\text{g}/\text{kg}/\text{hr} = 295.7 \text{ nmol}/\text{kg}/\text{h}$)

- **Primary endpoint IV GIR:** Values from SDTM.EX where EXTRT="IV GLUCOSE INFUSION", not including the "IV GLUCOSE BOLUS".
- **Total amount of carbohydrates received:**

Calculated as the sum of carbohydrates received via IV glucose infusion or bolus, as part of total parenteral nutrition, via oral route and via NG tube or gastrostomy. This average daily value will be used in analysis calculated as the sum of carbohydrates received divided by number of days in corresponding period. As IV glucose infusion is recorded in mg/kg/min, for each analysis period, the total amount received will be calculated as:

$$\text{IV glucose infusion (mg)} = \text{Infusion rate recorded in CRF} \times \text{WGT} \times \text{TIME}$$

with WGT = weight at beginning of the analysis period, TIME = duration of analysis period in minutes

IV glucose infusion or bolus are reported in SDTM.EX with EXTRT in "IV GLUCOSE INFUSION" or "IV GLUCOSE BOLUS".

Carbohydrates received via oral route, via NG tube or gastrostomy are reported under Carbohydrates administration eCRF.

Total parenteral nutrition is reported under Carbohydrates administration eCRF selecting observations specified as part of TPN.

- **Nightly gastric carbohydrates to treat hypoglycemia** = amount of gastric carbohydrates (g) given between midnight and 6 am inclusive to treat hypoglycemia.
- **Gastric carbohydrates received to treat hypoglycemia:** those will be the Carbohydrates received via NG tube or gastrostomy reported under Carbohydrate's administration eCRF and identified as used to treat a hypoglycemic episode in the same eCRF form. Oral route carbohydrates are not included in this endpoint.
- **SMPG-detected Hypoglycemia episodes** = PG <70 mg/dL or 3.9 mmol/L, reported in the eCRF. A single hypoglycemia episode is defined as up until 60 minutes from the start of the episode even if normoglycemia (>70 mg/dL) is not reached within this time. A new episode of hypoglycemia is to be reported when the next PG value below 70 mg/dL (3.9 mmol/L) is measured. No programming is needed to detect the events as they are reported in the eCRF.
- **SMPG-detected Clinically significant hypoglycemia episode** = PG <54 mg/dL or 3.0 mmol/L, reported in the eCRF. A single clinically significant hypoglycemia episode is defined as up until 60 minutes from the start of the episode even if normoglycemia (>54

mg/dL) is not reached within this time. A new episode of clinically significant hypoglycemia is to be reported when the next PG value below 54 mg/dL (3.0 mmol/L) is measured. No programming is needed to detect event as they are reported in the eCRF.

- **CGM-detected Hypoglycemic episode** = PG <70 mg/dL (3.9 mmol/L) for 15 minutes or more, as measured from external data. A single hypoglycemia episode is defined as up until 60 minutes from the start of the episode even if normoglycemia (>70 mg/dL) is not reached within this time. A new episode of hypoglycemia is to be reported when the next PG value below 70 mg/dL (3.9 mmol/L) is measured. Event will be defined by programming using external CGM data.
- **CGM-detected Clinically significant hypoglycemia episode** = PG <54 mg/dL or 3.0 mmol/L for 15 minutes or more, as measured from external data. A single clinically significant hypoglycemia episode is defined as up until 60 minutes from the start of the episode even if normoglycemia (>54 mg/dL) is not reached within this time. A new episode of clinically significant hypoglycemia is to be reported when the next PG value below 54 mg/dL (3.0 mmol/L) is measured. Event will be defined by programming using external CGM data.
- **Event rate** = average of the weekly number (sum) of events/episodes, based on the number of weeks in the relevant period. Events include hypoglycemia, clinically significant hypoglycemia, gastric carbohydrate administrations, and SMPG readings.
- **Percent time (CGM)** = (number of minutes where PG at a pre-defined level / total number of minutes patient is wearing CGM) * 100%. For this calculation, one assessment of CGM will be considered having a 5-minute duration. The possible levels are:
 - **In range:** PG between 70-180 mg/dL (3.9-10.0 mmol/L), inclusive
 - **Hypoglycemia:** PG <70 mg/dL (3.09 mmol/L)
 - **Clinically significant hypoglycemia:** PG <54 mg/dL (3.0 mmol/L)
 - **Hyperglycemia:** PG >180 mg/dL (10.0 mmol/L)
- **Time to complete weaning off IV GIR:** Time from first exposure during Part 2 to stop of Glucose infusion. Complete weaning off IV GIR is defined as the first point in time when the patient has been off IV GIR for 12 hours. This definition is based on clinical considerations that 12 hours off IV GIR is considered a reasonable indication that patients can manage without IV GIR, even though some of them may need re-initiation of IV glucose at later point. In case of study withdrawal before having the event, patient will be censored at time of study withdrawal.
- **Time to actual hospital discharge:** Time from first exposure during Part 2 to discharge of hospital. In case of study withdrawal before having the event, patient will be censored at time of study withdrawal.

- **Time to pancreatic surgery** = Time from first exposure during Part 2 to pancreatic surgery. Pancreatic surgery event will be retrieved from Adverse Event or Medical History Form. Pancreatic surgery is defined as sub-total or total pancreatectomy with a cutoff of 95% or more. In case of study withdrawal before having the event, patient will be censored at time of study withdrawal.
- **Extent of hypoglycemia (AO_C_{glucose})** =

$$\sum_{k=0}^{X-1} \frac{(UL - PG_k) + (UL - PG_{k+1})}{2} \times (t_{k+1} - t_k)$$

where UL is the upper limit for the hypoglycemia definition (70 mg/dL or 54 mg/dL); k is the k^{th} time point that glucose is measured using CGM; PG_k is the PG value in mg/dL on the k^{th} time point; and X is the end time point of the 3-week treatment period (Weeks 2-4). When $k = 0$, t_k is set to 0 and PG_k is the PG value corresponding to the start of the 3-week treatment period. Only PG values less than UL will be included in the calculation. If $PG \geq UL$ at the k^{th} time point and $PG < UL$ at the $k^{\text{th}}+1$ time point, then the extent of hypoglycemia for that interval will be determined as follows:

1. Estimate time point on x-axis where $PG = UL - 0.01$, as if a straight line were drawn between time points by using the following formula:

$$\hat{k} = \frac{(UL - 0.01) - b}{m}$$

Where b = y-intercept of line created by the coordinates (k^{th} time point, PG_k) and ($k^{\text{th}}+1$ time point, PG_{k+1}) and m = slope of that line.

2. Substituting PG_k with UL and t_k with $t_{\hat{k}}$, the formula for the estimated interval below UL is as follows:

$$\frac{(UL - UL) + (UL - PG_{k+1})}{2} \times (t_{k+1} - t_{\hat{k}})$$

Similar methodology would be utilized if $PG < UL$ at the k^{th} time point and $PG \geq UL$ at the $k^{\text{th}}+1$ time point, with the estimate of the time point where PG crosses the UL threshhold being estimated for $t_{\hat{k}+1}$.

If the time period between two timepoints is greater than 1 hour then no interpolation will be performed and no area will be calculated over this timeperiod.

If PG results from the k^{th} time point are missing, then $k-1$ scores will be used and the weight will be $t_{k+1}-t_{k-1}$.

The extent of hypoglycemia calculated as above will then be divided by the total duration of CGM assessments calculating as summing all $t_{k+1}-t_k$ duration used in previous formulae. Time points for which $PG>UL$ will be included in the total duration. This variable will then be used the endpoint evaluation.

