8. TRIAL DESIGN

8.1. Overall Trial Design and Plan

This is a combined phase 2 and 3, randomized, multinational trial to evaluate the efficacy and safety of individually titrated dasiglucagon in children ≥ 7 days and < 1 year of age who have been diagnosed with CHI, comprising 2 parts, a crossover (2 periods, 48 hours each), double-blind, placebo-controlled Part 1, and an open-label, single-arm Part 2 of 21 days (Figure 1).

Abbreviations: Min = minimum

Figure 1 Design of Trial ZP4207-17103

After screening, eligible patients will complete a minimum 24-hour run-in period to confirm the IV glucose randomization requirement (≥ 10 mg/kg/min). All non-nutritional carbohydrates and carbohydrate fortification of feeds are prohibited during this 24-hour run-in period. After the run-in period, patients will be randomly assigned in a double-blind fashion to receive dasiglucagon or placebo for 48 hours, after which they will be crossed over to the other trial treatment for an additional 48 hours. At the time of crossover, the trial drug will be initiated from the starting dose of 10 μ g/hr, and IV GIR will be set to the rate obtained at the end of the run-in period and titrated accordingly.

There will be no washout between the 2 periods in Part 1 to limit the length of time in which patients are reliant on IV GIR as their only means of preventing/treating hypoglycemia. This is deemed acceptable because:

- The half-life ($t_{1/2}$) of dasiglucagon is short (~30 minutes, for the 0.6 mg dose, and potentially shorter for lower doses, ~22 minutes) relative to the 48-hour duration of each crossover

period. Moreover, for the primary endpoint, only the last 12 hours of the 48-hour period will be used for endpoint assessment.

- Assuming a positive effect of dasiglucagon, the absence of washout is conservative with respect to key secondary endpoints since a potential carry over effect of dasiglucagon in Period 2 is attributed to placebo.

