9.4. Treatment Discontinuation

To prevent missing data, patients should, to the extent possible, be kept in the trial; therefore, treatment discontinuation is often the preferred option in case of, e.g., substantial noncompliance with trial procedures or initiation of prohibited treatment that interferes with the efficacy and safety evaluation. If it is an investigator's decision to discontinue the patient's treatment, the investigator should, whenever possible, discuss the potential discontinuation of the treatment with the medical monitor. If the patient is discontinued from trial treatment by the investigator or by parent/guardian's decision, the reason for treatment discontinuation and the date of treatment discontinuation will be recorded on the appropriate page of the eCRF. The patient should be asked to continue in the trial by following the planned visit schedule and to have trial assessments performed according to the Schedule of Events. This is especially important during Part 1 of the trial where the primary endpoint is evaluated. As a minimum, the patient will be asked to attend the Follow-up Visit 28 days (\pm 3 days) after discontinuation of trial treatment.

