6.1.4. Handling of Dropouts or Missing Data

6.1.4.1. Premature Withdrawal from Trial Treatment

If the patient is discontinued from trial treatment, he/she (or the parent) should be asked to continue in the trial by following the planned visit schedule and to have trial assessments performed according to the schedule of events. This is especially important during Part 1 of the trial where the primary endpoint is evaluated. As a minimum, the patient (or the parent) will be asked to attend the Follow-up Visit 28 days (\pm 3 days) after discontinuation of trial treatment.

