7.4. Exposure and Compliance

Study drug administration will be summarized separately for total dasiglucagon exposure ($\mu\text{g}/\text{kg}$) and length of exposure (days), respectively for Part 1 and Part 2. Moreover, the duration of drug use (days) will be presented. It will be calculated as length of exposure minus number of days without IMP exposure. Additionally, the infusion rate, defined as the average hourly weight-adjusted infusion rate of study drug over the study period analyzed (i.e., $\mu\text{g}/\text{kg}/\text{hr}$ and $\mu\text{g}/\text{hr}$), will be summarized for each Part. For Part 1, the two days of duration will be used for calculation and for Part 2, it will be calculated for each week.

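### SAP Table 4 ends each Part 1 period, and its primary 12-hour window, at last exposure, so a patient who stops trial drug early but stays in the trial is scored on treatment, against the treatment-policy estimand

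*SAP*

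**What the plan says.** SAP section 6.1.7 explains that GIR is recorded continuously, so periods have to be derived. Of these periods it says: "Those will then be used to assign a treatment period to an evaluation". Table 4 then gives the limits:

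- Period 1 ends at "Last exposure treatment period 1", and period 2 at the corresponding last exposure.
- The last-12-hour window within each period ends at that same date and starts at "End date minus 12 hours/24 hours".
- No cell sets an end at 48 hours, although the list just above the table labels the two periods as 48 hours long.

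Other parts of the plan point the other way:

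- Protocol section 8.1: "only the last 12 hours of the 48-hour period will be used for endpoint assessment".
- SAP section 8.1 and Protocol section 13.4.3.1 define a treatment-policy estimand. The SAP adds in parentheses that data recorded off treatment count.
- SAP section 8.1.1 says, for the complete-case analysis, that an off-treatment assessment is not a missing one.
- Protocol section 9.4: "treatment discontinuation is often the preferred option in case of, e.g., substantial noncompliance with trial procedures or initiation of prohibited treatment". SAP section 6.1.4.1 says of a patient taken off trial treatment: "he/she (or the parent) should be asked to continue in the trial by following the planned visit schedule". Both stress Part 1, where the primary endpoint is measured.

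SAP section 10, which lists changes from the planned analysis, does not mention an exposure-based window.

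**The concern.** The trial asks sites to keep observing patients who stop drug, so that Part 1 GIR is available for them. Table 4 then excludes that GIR from the primary endpoint. For a permanent early stopper the window contains no time after the last dose. GIR recorded after loss of effect, or under another therapy, is what a treatment-policy analysis is meant to use, and it drops out.

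The same period limits feed other Part 1 endpoints. The 48-hour weighted mean GIR is computed within them. The endpoint of GIR below 10 mg/kg/min uses the same 12-hour value. Total carbohydrates are averaged over the analysis period in SAP section 6.1.7.

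With 12 patients, one such case is 8% of the sample. If the conflict is noticed only after unblinding, choosing between the two windows becomes a post hoc decision on the primary endpoint.

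**Working it through.** **1. Planning inputs (SAP section 3.2).** Mean difference 7.5 mg/kg/min, SD of differences 7.36, n = 12, two-sided alpha 0.05.

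- Standard error = 7.36/√12 = 2.12.
- Noncentrality = 7.5/2.12 = 3.53 on 11 df. The exact one-sample t-test power is 89.4%, against 89% stated, so the plan's figure reproduces.

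**2. What exposure means.** SAP section 7.4 defines duration of drug use as "length of exposure minus number of days without IMP exposure". SAP section 6.1.7 times weaning as "Time from first exposure during Part 2 to stop of Glucose infusion", which treats first exposure and the glucose infusion as separate things. Table 4 starts Part 2 at first exposure on Day 5, when IV glucose would ordinarily already be running. All three fit trial drug. However, SAP section 6.1.7 also stores IV glucose records in the SDTM exposure domain, and Table 4 does not name the drug.

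**3. The two windows.** Let s be the hour of the last dose within a period. Table 4 uses s−12 to s; the protocol's window is hours 36 to 48. Overlap = max(0, s−36) hours. Off-drug hours in the protocol window = 48 − max(s, 36).

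| Last dose (h) | Table 4 window | Overlap (h) | Off-drug hours in 36–48 |
|---|---|---|---|
| 6 | −6 to 6 | 0 | 12 |
| 24 | 12 to 24 | 0 | 12 |
| 36 | 24 to 36 | 0 | 12 |
| 42 | 30 to 42 | 6 | 6 |
| 48 | 36 to 48 | 12 | 0 |

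The Table 4 window always holds zero hours after the last dose. For a stop before hour 12 it also reaches back before its own period: into run-in for period 1, or into the other treatment for period 2. The windows coincide only when drug runs to hour 48.

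**4. Illustrative size.** Assumptions: k patients stop dasiglucagon at s between 24 and 48; each has the full 7.5 effect in the Table 4 window; each keeps a share r of it off drug; placebo values are unaffected.

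- Table 4 scores 7.5.
- The treatment-policy value is 7.5r for s ≤ 36, and 7.5[(s−36) + r(48−s)]/12 for s > 36.
- Shift in the mean difference = k × (7.5 − treatment-policy value)/12.

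Results:

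- s = 24 to 36, k = 1: r = 0.5 gives 3.75/12 = 0.31; r = 0 gives 7.5/12 = 0.63.
- s = 42, k = 1: r = 0.5 gives (7.5 − 5.625)/12 = 0.16; r = 0 gives (7.5 − 3.75)/12 = 0.31.
- s = 48: 0.

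For one patient stopping by hour 36 the shift is 4% to 8% of 7.5. In planning standard errors it is 0.31/2.12 = 0.15 to 0.63/2.12 = 0.29.

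**5. Do other rules catch it?** No. The imputation in SAP section 8.1 and the imputation-based and tipping-point analyses in 8.1.1 act on missing values. Under Table 4 an early stopper's value is present, so none of them is triggered.

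**The case against.** The strongest reply is that this is loose wording rather than a planned on-treatment analysis. The periods are labelled as 48 hours, the estimand text is explicit, and exposure could be read more widely because IV glucose is stored in the same data domain. The statement of intent stands, and a reader who inferred that the sponsor means to abandon treatment policy would go further than the documents allow. But Table 4 is the stated derivation of those labelled periods, and a programmer will follow it. The alternative reading does not help: ending the window at the last glucose infusion would discard time at zero GIR after weaning.

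A second reply is that permanent stops within a 48-hour inpatient period may be rare. That also stands. Protocol section 9.4 prefers stopping drug to leaving the trial; it does not say that stopping is frequent. The low drop-out expected in section 20.4.3 of the German protocol concerns leaving the trial, so it does not settle the matter either way.

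A third is that the carbohydrate endpoint is less clearly affected. SAP section 8.2.1 divides by the number of days followed, which is follow-up wording. The effect there comes only through the period definition in section 6.1.7, and daily averaging may soften it.

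Finally, a reader might infer that Table 4 always favours dasiglucagon. The documents do not support that. The direction depends on when the patient stops, in which period, and what happens to GIR afterwards. An opposite case built on effect proportional to dose would conflict with Protocol section 10.7, which expects a medium response at the lowest dose. Having a newly started CHI treatment restore full control would conflict with section 10.11.2, which bars new CHI treatment in Part 1. Other patterns are therefore left unquantified.

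**Conclusion.** The concern holds for a patient who permanently stops trial drug before the end of a Part 1 period and stays under assessment. For that patient Table 4 gives an on-treatment primary value, contrary to SAP sections 8.1 and 8.1.1 and to the 48-hour window in Protocol section 8.1. A temporary interruption followed by resumption is still captured, and a patient dosed to the end of the period is unaffected.

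The size is conditional. With no early stoppers it is zero. The 0.31 to 0.63 mg/kg/min is an illustration for one of 12, resting on an assumed full planning effect before the stop and half or none after it; it is not a forecast. It is a shift in the estimate, and at well under one standard error it gives no ground to infer that the primary conclusion would change. It should be fixed because a stated rule gives the wrong primary value for a case the protocol foresees.

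**What to change.** In Table 4:

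- End each Part 1 period at the earliest of 48 hours after its start, the start of the next period (next trial drug or the associated reset of GIR to the run-in rate), or withdrawal from the trial, regardless of trial-drug exposure. The cut-off at the next period matters because an early crossover would otherwise bring reset GIR values into the previous window.
- If period 2 drug is never started, begin period 2 at the scheduled crossover.
- Take the primary window as the last 12 hours of that interval, never reaching before the start of its own period.
- Use all valid GIR records whatever the drug status, and keep the site 101 exclusion in SAP section 8.1.
- Apply the same limits to the 48-hour GIR, the below-10 mg/kg/min endpoint and total carbohydrates.
- Name the drug wherever exposure is used. State when a period cut short by trial withdrawal counts as missing, so that the section 8.1 imputation applies.
- Keep a last-exposure window, if wanted, only as a labelled on-treatment supplementary analysis.

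The cost is a table edit and minor reprogramming before unblinding. No new data are needed, because patients who stop drug are already asked to stay under assessment. The estimate may be slightly less favourable if a responder stops dasiglucagon early.

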6.3. Dasiglucagon for the Treatment of Congenital Hyperinsulinism

6.3.1. Dasiglucagon

Dasiglucagon is a peptide analog of human glucagon in development for the treatment and prevention of hypoglycemia in patients with diabetes mellitus and CHI via SC or intramuscular (IM) administration. Dasiglucagon is a stable analog of glucagon that has been specifically designed to overcome the issues with fibril formation and instability in solution observed with marketed glucagon products. Compared to native human glucagon, dasiglucagon also comprises 29 amino acids. As a result of chemical modifications (7 amino acid substitutions compared to human glucagon), the pronounced tendency of glucagon to form fibrils and aggregate has been effectively prevented in dasiglucagon. In addition, the chemical stability in aqueous media at physiological pH has been improved.

To support the use of dasiglucagon in the pump for this trial, compatibility/in-use studies have been performed with dasiglucagon 4 mg/mL in Roche Accu-Chek® Combo pump using the Accu-Chek® Spirit 3.15 mL cartridge system and the Accu-Chek® FlexLink infusion set. The studies support an in-use time for up to 6 days at 37°C.

Dasiglucagon has been granted orphan drug designation by the European Commission on 20 June 2017 for the '*treatment of congenital hyperinsulinism*.' Furthermore, the FDA granted an orphan drug designation for the '*treatment of hypoglycemia in patients with congenital hyperinsulinism (CHI)*' on 10 August 2017.

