10.7. Selection of Doses in the Trial

Both the starting dose and the maximum allowed doses are based on experience with marketed glucagon products in this patient population.¹¹

At present, no pediatric PK data are available for dasiglucagon. However, an approximate estimation of expected drug concentration in a 3 kg patient has been made by extrapolation of a previously made PK model for pediatric patients with weights between 25 and 45 kg.¹⁷

In this trial, dasiglucagon will be titrated to meet the needs of the individual patient on the basis of PD effects in regards to efficacy and tolerability, and it is expected that the majority of patients will be adequately treated with a dasiglucagon infusion rate of approximately 20 to 40 µg/hr. The up-titration will stop when IV glucose is completely weaned, if undesirable side effects arise, or when no additional PD effects are observed as the dasiglucagon infusion rate is increased.

Based on the current PK/PD model, the predicted plasma concentration is expected to result in a medium PD response at the lowest dose level and be approaching maximum effect at the highest dose level. The PD response of patients will be monitored closely in this trial, and the appropriateness of the applied titration algorithm will be evaluated.

Although the PK of dasiglucagon has been shown to be dose-proportional in adults and in all toxicologically tested species over a wide range of doses, limited PK sampling at each dose level is planned based on the limited available blood volume in this population.

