2.2.3. Pharmacokinetic Variable(s)

For all subjects, blood samples will be collected twice during the trial to measure for dasiglucagon levels at steady-state on Day 6 and Day 25. PK Sampling for drug exposure at Visit 5 is only applicable for patients with a body weight of ≥ 4 kg.

3. Overall Study Design and Plan

This is a combined phase 2 and 3, randomized, multinational trial to evaluate the efficacy and safety of individually titrated dasiglucagon in children ≥ 7 days and <1 year of age who have been diagnosed with CHI, comprising 2 parts, a crossover (2 periods, 48 hours each), double-blind, placebo-controlled Part 1, and an open-label, single-arm Part 2 of 21 days.

After screening, eligible patients will complete a minimum 24-hour run-in period to confirm the IV glucose randomization requirement (≥ 10 mg/kg/min). All non-nutritional carbohydrates and carbohydrate fortification of feeds are prohibited during this 24-hour run-in period. After the run-in period, patients will be randomly assigned in a double-blind fashion to receive dasiglucagon or placebo for 48 hours, after which they will be crossed over to the other trial treatment for an additional 48 hours. At the time of crossover, the trial drug will be initiated from the starting dose of 10 μ g/hr, and IV GIR will be set to the rate obtained at the end of the run-in period which corresponds to the last value obtained before randomization.

and titrated accordingly.

[figure not shown]
There will be no washout between the 2 periods in Part 1 to limit the length of time in which patients are reliant on IV GIR as their only means of preventing/treating hypoglycemia.

During Part 1, the trial drug and IV GIR should be adjusted according to the protocol-specified algorithm. Non-nutritional carbohydrates and/or carbohydrate fortification of feeds during Part 1 is only allowed when the maximum tolerable volume and concentration of IV glucose for the patient is reached, and should be limited to the minimum needed to ensure the patient's safety. All feedings (administered as parenteral nutrition, by nasogastric [NG] tube, gastrostomy, or normal route), will be recorded during this period.

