11.1. Pharmacokinetic Analysis

Plasma concentrations are collected on Day 5 (applicable for patients with a body weight of $\geq 4\text{kg}$, sample will only be collected if it does not compromise the total amount of blood drawn), Day 6 and Day 25. Descriptive summaries will be presented for plasma PK concentrations by study visit and infusion rate (in $\mu\text{g}/\text{kg}/\text{hr}$). Information pertaining to PK data collection will be listed.

PK analysis will be performed using PK population according to actual treatment received.

12. References

1. US Federal Register. (1998) International Conference on Harmonization; Guidance on Statistical Principles for Clinical Trials. Department of Health and Human Services: Food and Drug Administration [Docket No. 97D-0174]. Federal Register Volume 63, Number 179, pages 49583-49598. September 16, 1998.
2. ASA. (2016) Ethical Guidelines for Statistical Practice. Prepared by the Committee on Professional Ethics, April 2016. <http://www.amstat.org/about/ethicalguidelines.cfm>
4. The Royal Statistical Society: Code of Conduct, 2014.

13. Tables, Listings, and Figures

All listings, tables, and graphs will have a header showing the sponsor company name and protocol and a footer showing the version of SAS, the file name and path, and the source of the data (CRF page or listing number).

The following reporting conventions will be adopted for the presentation of study data. These conventions will enhance the review process and help to standardize the presentation with common notations.

General Reporting Conventions

- All tables and data listings will be developed in landscape orientation.
- Specialized text styles, such as bolding, italics, borders, shading, and superscripted and subscripted text will not be used in tables, figures, and data listings unless they add significant value to the table, figure, or data listing.
- Only standard keyboard characters should be used in tables and data listings. Special characters, such as nonprintable control characters, printer-specific characters, or font specific characters, will not be used on a table, figure, or data listing.

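### The µg-to-molar conversion in the SAP's clearance definition is off by a factor of 1,000 as printed: nmol should read pmol

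*SAP*

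**What the plan says.** SAP 6.1.7 (Derived Variables, PK Clearance) sets CL/f in L/h equal to R0/Css. R0 is the "infusion rate (pmol/h) and" Css is the "concentration at steady state (pmol/L), weight"; the last word hangs there without a definition. A bracketed helper follows, which equates 1 µg/kg/hr with "295.7 \text{ nmol}/\text{kg}/\text{h" (the markup comes from the PDF reading of an equation).

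Three other places bear on it:

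- Protocol 6.3.1 on the size of the molecule: "Compared to native human glucagon, dasiglucagon also comprises 29 amino acids".
- SAP 2.2.3 on the PK variables: "blood samples will be collected twice during the trial to measure for dasiglucagon levels at steady-state on Day 6 and Day 25".
- SAP 11.1 on PK reporting: "Descriptive summaries will be presented for plasma PK concentrations by study visit and infusion rate".

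Neither document states a molar mass. Infusion rates are in mass units throughout: µg/hr in Protocol 10.2, µg/kg/hr and µg/hr in SAP 7.4, and µg/kg/hr in SAP 11.1.

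**The concern.** A mass-to-mole conversion fixes a molar mass, and the one printed fixes a value that no peptide can have. It is also in nmol, while both terms of the formula it serves are in pmol.

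Doses are recorded in µg and the formula needs pmol/h, so this line is the only bridge between them in the plan. A programmer or a QC reader has no stated molar mass to check it against. Read literally and scaled to the unit of R0, it inflates every clearance by the same factor of 1,000.

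**Working it through.** **Inputs from the documents**

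- Helper: 1 µg/kg/h = 295.7 nmol/kg/h (SAP 6.1.7).
- Units: R0 in pmol/h, Css in pmol/L, CL/f in L/h (SAP 6.1.7).
- Molecule: 29 amino acids (Protocol 6.3.1).
- Rates expected for most patients: 20 to 40 µg/hr (Protocol 10.7).

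**Assumptions from general chemistry, not in the documents**

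- A hydrogen atom is about 1 g/mol.
- A typical amino-acid residue is 100 to 130 g/mol. The lightest standard residue is 57 and the heaviest 186 g/mol. One water (18 g/mol) is added per peptide.

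**Step 1. Formula check.** (pmol/h) / (pmol/L) = L/h. The clearance formula is dimensionally right, so only the helper is in question.

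**Step 2. Molar mass implied by the helper.** The kg and h cancel, so molar mass = mass / amount.

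| Unit given to 295.7 | Calculation | Molar mass (g/mol) | Per residue (÷ 29) |
|---|---|---|---|
| nmol (as printed) | 1e-6 / 295.7e-9 | 3.38 | 0.117 |
| pmol | 1e-6 / 295.7e-12 | 3,382 | 116.6 |
| µmol | 1e-6 / 295.7e-6 | 0.0034 | 0.00012 |

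The printed version puts each residue below the mass of one hydrogen atom. Of the three prefixes, only pmol is possible.

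**Step 3. What 1 µg of a 29-residue peptide should be.** Molar mass = 29 × residue mass + 18, and pmol per µg = 1e6 / molar mass.

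- Typical residues (100 to 130): 2,918 to 3,788 g/mol, so 343 down to 264 pmol per µg.
- Absolute bounds (57 to 186): 1,671 to 5,412 g/mol, so 598 down to 185 pmol per µg.

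295.7 pmol lies inside both ranges. The printed 295.7 nmol is 295,700 pmol. Against the absolute bounds that is 295,700/598 to 295,700/185, or about 500 to 1,600 times too large.

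**Step 4. Effect on R0 and CL/f.**

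| Rate | 295.7 taken as pmol | nmol followed, then scaled to pmol |
|---|---|---|
| 20 µg/hr | 20 × 295.7 = 5,914 pmol/h | 5,914,000 pmol/h |
| 40 µg/hr | 40 × 295.7 = 11,828 pmol/h | 11,828,000 pmol/h |

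Css is measured and does not pass through the helper. CL/f is therefore 1,000 times too high in the second column, whatever Css is.

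**Step 5. Body weight.** The helper is per kg and R0 is not, so a per-kg rate has to be multiplied by weight. At an assumed 3 kg and 30 µg/h, the direct route gives 30 × 295.7 = 8,871 pmol/h. The per-kg route gives (30/3) × 3 × 295.7 = 8,871 pmol/h. The two agree, and the units of R0 already require the multiplication, so there is no separate weight error.

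**The case against.** Four points can be made for the plan.

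1. **The wrong symbol may be on the other side.** If the left side were meant as 1 mg/kg/h, then 1e-3 / 295.7e-9 = 3,382 g/mol and nmol would be right. This does not change the repair. One mg = 295.7 nmol is the same relation as 1 µg = 295.7 pmol, and the plan gives its rates in µg.

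2. **The PDF reading may have altered a letter.** The helper is a typeset equation, while the neighbouring pmol units are ordinary text. That those were read cleanly is only weak reassurance. This stands: one prefix letter carries the finding, so the source page has to be checked before anything is changed.

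3. **The formula already tells the programmer what unit is needed.** Anyone who enters 295.7 to obtain R0 in pmol/h gets the right answer. A clearance 1,000 times too high might well be noticed. This makes the error conditional, but a prespecified derivation should not be correct only when its printed unit is ignored.

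4. **No listed output uses it.** SAP 2.2.3 and SAP 11.1 name concentrations, not clearance. This stands, and it limits the severity. CL/f is still a defined derived variable and may be reported.

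**Conclusion.** The helper is wrong as printed, and the point is minor. The two sides of the conversion disagree by a factor of 1,000, and replacing nmol with pmol removes the disagreement. If the printed unit is followed, CL/f is overstated 1,000-fold; if 295.7 is used directly as pmol, there is no error. Efficacy, safety, alpha and sample size are untouched.

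This rests on two assumptions. The first is that the prefix was read correctly from the PDF. The second is that the digits 295.7 are right: the 29-residue check confirms the order of magnitude but not the digits, because the documents give no molar mass.

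**What to change.** Check the source page of SAP 6.1.7 for the prefix, and check 295.7 against the molar mass of dasiglucagon. If the page does read nmol, change the helper to 1 µg/kg/h = 295.7 pmol/kg/h. State the molar mass beside it, and write the step out in full: R0 (pmol/h) = rate (µg/h) × 295.7, equivalently rate (µg/kg/h) × weight (kg) × 295.7. That also gives the stray word after the Css unit a meaning.

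The cost is one line in the SAP. Conduct, data collection and sample size are unaffected. If the page already reads pmol, no correction is needed.
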